Appendix 1. Abbreviations

This following is a list of abbreviations that may be used in the protocol.

Abbreviation	Term
AA	Accelerated Approval
ACIP	Advisory Committee on Immunization Practices
AE	adverse event
AlPO ₄	aluminum phosphate
ALT	alanine aminotransferase
AST	aspartate aminotransferase
bivalent rLP2086	bivalent recombinant lipoprotein 2086 vaccine (Trumenba)
CDC	Centers for Disease Control and Prevention
CFR	Code of Federal Regulations
CI	confidence interval
CK	creatine kinase
CRF	case report form
CRM	cross-reactive material
CSA	clinical study agreement
CT	clinical trial
CTA	clinical trial application
DILI	drug-induced liver injury
DTaP, dTaP	diphtheria, tetanus, and acellular pertussis vaccine
DU	dispensable unit
EC	ethics committee
e-diary	electronic diary
EDMC	external data monitoring committee
EDP	exposure during pregnancy
EU	European Union
EudraCT	European Clinical Trials Database
FDA	Food and Drug Administration (United States)
fHBP	factor H binding protein
GCP	Good Clinical Practice
GGT	gamma-glutamyl transferase
GMT	geometric mean titer
GSK	GlaxoSmithKline
HBV	hepatitis B virus
Hib	Haemophilus influenzae type b
HPV4	quadrivalent human papillomavirus vaccine
hSBA	serum bactericidal assay using human complement
hSBA-MenA	serum bactericidal assay using human complement to measure activity against Neisseria meningitidis group A

Abbreviation	Term
hSBA-MenA/C/W/Y	serum bactericidal assay using human complement to measure activity against Neisseria meningitidis group A, group C, group W, and/or group Y
hSBA-MenC	serum bactericidal assay using human complement to measure activity against Neisseria meningitidis group C
hSBA-MenW	serum bactericidal assay using human complement to measure activity against Neisseria meningitidis group W
hSBA-MenY	serum bactericidal assay using human complement to measure activity against Neisseria meningitidis group Y
IB	investigator's brochure
ICD	informed consent document
ICH	International Council for Harmonisation
ID	identification
IMD	invasive meningococcal disease
IND	investigational new drug application
INR	international normalized ratio
IP	investigational product
IPV	inactivated poliomyelitis virus
IRB	institutional review board
IRC	independent review committee
IRT	interactive response technology
ISC	independent statistical center
ITT	intent-to-treat
IUD	intrauterine device
IVRS	interactive voice response system
IWRS	interactive Web-based response system
LCI	lower limit of the confidence interval
LFT	liver function test
LLOQ	lower limit of quantitation
LOD	limit of detection
LP2086	lipoprotein 2086
LSLV	last subject last visit
MCV4	quadrivalent meningococcal polysaccharide conjugate
MedDRA	Medical Dictionary for Regulatory Activities
MenA	Neisseria meningitidis group A
MenABCWY	Neisseria meningitidis group A, B, C, W, and Y vaccine
MenACWY	meningococcal groups A, C, W, and Y conjugate vaccine
MenA/C/W/Y	Neisseria meningitidis group A, group C, group W, and/or group Y
MenACWY-CRM	meningococcal group A, C, W-135, and Y conjugate vaccine (Menveo)
MenACWY-TT	meningococcal polysaccharide groups A, C, W-135, and Y tetanus toxoid conjugate vaccine (Nimenrix)
MenB	Neisseria meningitidis group B
MenC	Neisseria meningitidis group C

Abbreviation	Term
MenCYW-135	meningococcal group C, Y, and W-135
MenW	Neisseria meningitidis group W
MenY	Neisseria meningitidis group Y
mITT	modified intent-to-treat
MnB	Neisseria meningitidis group B
N/A	not applicable
OMV	outer membrane vesicle
PAR	postapproval requirement
PCD	primary completion date
PI	principal investigator
PRP-OMP	polyribosylribitol phosphate oligosaccharide of Haemophilus influenzae type b conjugated to outer membrane protein
PT	prothrombin time
rLP2086	recombinant lipoprotein 2086
RRI	research-related injury
rSBA	serum bactericidal assay using rabbit complement
rSBA-MenA	serum bactericidal assay using rabbit complement to measure activity against Neisseria meningitidis group A
rSBA-MenC	serum bactericidal assay using rabbit complement to measure activity against Neisseria meningitidis group C
rSBA-MenW	serum bactericidal assay using rabbit complement to measure activity against Neisseria meningitidis group W
rSBA-MenY	serum bactericidal assay using rabbit complement to measure activity against Neisseria meningitidis group Y
SAE	serious adverse event
SAP	statistical analysis plan
SBA	serum bactericidal assay
SRM	study reference manual
SRSD	single reference safety document
TBili	total bilirubin
Tdap	tetanus, low-dose diphtheria, and low-dose acellular pertussis
ULN	upper limit of normal
US	United States

Document Approval Record

Document Name:

B1971057 Clinical Protocol Amendment 2, Clean Copy, 09 Jul 19

Document Title:

## 1. VERSION HISTORY

This statistical analysis plan (SAP) Version 4 for Study B1971057 is based on protocol amendment 2 dated 09 Jul 2019.

**Table 1. Summary of Major Changes in SAP Amendments**

Version / Date	Associated Protocol Amendment	Rationale	Specific Changes
1 21MAR2017	Final, 16JAN2017	Original SAP	N/A
2 15FEB2018	Amendment 1, 23AUG2017	Protocol Amendment	
 
Updated the covariates for the subgroup analysis.
 
Updated to include the pilot safety population in the Stage 1 safety population.
 
Updated to remove the presentation of p-values in the safety summaries.
 
Added the requirement to perform mixed-effects model with repeated measures (MMRM)/generalized linear mixed-effects model with repeated measures (GLIMMIX) analyses on immunogenicity data.
 
Clarified the methods used in the noninferiority (NI) analyses. Added the criteria for NI analyses.
 
Added section for additional immunogenicity analyses.
 
Updated the derivation of age at vaccination to follow prior Trumenba® studies.
 

3 29OCT2018	Amendment 1, 23AUG2017	Regulatory input, Clarification Clinical team input	
 
Added sensitivity analysis for composite response to address regulatory request.
 
Clarified the modified intent-to-treat (mITT) population definition.
 
Added the lower limits of quantitation (LLOQs) for Neisseria meningitidis group A, group C, group W, and/or group Y (MenA/C/W/Y) assays and for secondary Neisseria meningitidis group B (MenB) strains.
 
Clarified race categorization in subgroup analyses.
 
Added planned positive predictive value (PPV) analyses for assessment of association between results for primary MenB and secondary MenB strains.
 
Added description of the variability assessment of ACWY data endpoints.
 
Removed previously included exploratory analyses.
 

**Table 1. Summary of Major Changes in SAP Amendments**

Version / Date	Associated Protocol Amendment	Rationale	Specific Changes
4 17MAY2021	Amendment 2, 09JUL2019	Protocol Amendment	
 
• Moved the booster dose safety endpoints from secondary to primary safety endpoints.
 
• Moved some immunogenicity endpoints (related to persistence evaluation) from secondary to exploratory endpoints.
 
• Removed the 1:4 endpoint for ACWY strains for the persistence and booster endpoints.
 
• Updated the Stage 2 enrollment, for ACWY-experienced subjects in addition to ACWY-naïve subjects to obtain data on the persistence of the immune response after 2 doses of Neisseria meningitidis group A, B, C, W, and Y vaccine (MenABCWY) as well as on the safety and immunogenicity of the booster response in individuals who had previously received an ACWY-containing vaccine.
 
• Removed the persistence and booster endpoints for defined titers; removed the persistence endpoints for geometric mean titers (GMTs).
 

5 28 Feb 2022	N/A	
Table reduction initiative, including reducing redundancy
 
Adding additional analyses
 
Administrative changes
	
 
• Removed from Stage 2 analyses the exploratory 4-fold rise and the composite response endpoint for MenB strains.
 
• Replaced some study conduct tables for Stage 2 with listings in Section 6.6.
 
• Added exploratory analyses for MenA/C/W/Y to investigate the relationship between the pre-booster dose and the post-booster dose titers in Section 6.4.
 
• Added in Section 7.1 a new planned reporting event performed when subjects have completed the 1-month postbooster blood draw.
 
• Updated the temperature scale of severity for fever for Stage 2 (Table 14) in Section 3.5.2.2 to allow for consistency in severity designation between temperatures recorded in Fahrenheit and Celsius.
 
• Added the definition of the booster safety population in Section 4.4.
 

## 2. INTRODUCTION

This SAP provides the detailed methodology for summary and statistical analyses of the data collected in Study B1971057. A brief description of the study design and the study objectives are given. Subsequent sections include analysis population and the definitions of the immunogenicity and safety endpoints followed by details around statistical analysis and reporting. A list of tables, listings, and figures, mock-up tables, listings, and figures, and programming rules are prepared separately based on the methods described in this document. This document may modify the plans outlined in the protocol; however, any major modifications of the primary endpoint definition or its analysis will also be reflected in a protocol amendment.

### 2.1. Study Objectives

#### 2.1.1. Primary Immunogenicity Objective

- To assess the immune response induced by bivalent recombinant lipoprotein 2086 vaccine (bivalent rLP2086) as measured by serum bactericidal assay using human complement (hSBA) performed with 4 primary MenB test strains, 2 expressing an rLP2086 subfamily A protein and 2 expressing an rLP2086 subfamily B protein, measured 1 month after the second vaccination, in the bivalent rLP2086 arms (Group 2 and 4 subjects) combined.

#### 2.1.2. Primary Safety Objective

- To describe the safety profile of bivalent rLP2086, as measured by local reactions, systemic events, adverse events (AEs), serious adverse events (SAEs), newly diagnosed chronic medical conditions (NDCMCs), medically attended AEs (MAEs), and immediate AEs, following Vaccinations 1 and 2 in the bivalent rLP2086 arms (Group 2 and 4 subjects) combined.
- To describe the safety profile of *Neisseria meningitidis* group A, B, C, W, and Y vaccine (MenABCWY), as measured by local reactions, systemic events, AEs, SAEs, NDCMCs, MAEs, and immediate AEs, after the booster vaccination.
- To describe the safety profile of bivalent rLP2086, as measured by local reactions, systemic events, AEs, SAEs, NDCMCs, MAEs, and immediate AEs, after the booster vaccination.

#### 2.1.3. Secondary Immunogenicity Objectives

- To describe the immune response induced by bivalent rLP2086 as measured by hSBA performed with 4 primary *Neisseria meningitidis* group B (MenB) test strains, 2 expressing an rLP2086 subfamily A protein and 2 expressing an rLP2086 subfamily B protein, measured 1 month after the second vaccination, in the bivalent rLP2086 arms (Group 2 and 4 subjects) combined.

- To describe the immune response induced by bivalent rLP2086 as measured by hSBA performed with secondary MenB test strains measured 1 month after the second vaccination in the bivalent rLP2086 arms (Group 2 and 4 subjects) combined.
- To describe the immune response induced by 1 dose of MenABCWY compared to the immune response induced by 1 dose of meningococcal groups A, C, Y, and W-135 oligosaccharide diphtheria conjugate vaccine (MenACWY-CRM), as measured by hSBA performed with ACWY test strains, in ACWY-naïve and ACWY-experienced subjects separately.
- To describe the immune response induced by 2 doses of MenABCWY compared to the immune response induced by 1 dose of MenACWY-CRM, as measured by hSBA performed with ACWY test strains, in ACWY-naïve and ACWY-experienced subjects separately.
- To describe the immune response induced by MenABCWY compared to the immune response induced by bivalent rLP2086 as measured by hSBA performed with 4 primary MenB test strains, 2 expressing an rLP2086 subfamily A protein and 2 expressing an LP2086 subfamily B protein, measured 1 month after the second vaccination in the ACWY-naïve and ACWY-experienced subjects combined.
- To describe the immune response induced by MenABCWY compared to the immune response induced by MenACWY-CRM and bivalent rLP2086 as measured by hSBA performed with ACWY test strains and 4 primary MenB test strains, 2 expressing an rLP2086 subfamily A protein and 2 expressing an LP2086 subfamily B protein, at blood sampling time points prior to the booster vaccination (Stage 1).
- To describe the immune response induced by MenABCWY compared to the immune response induced by MenACWY-CRM and bivalent rLP2086, as measured by hSBA performed with ACWY test strains and 4 primary MenB test strains, 2 expressing an LP2086 subfamily A protein and 2 expressing an LP2086 subfamily B protein, at blood sampling time points prior to the booster vaccination (Stage 2).
- To describe the immune response induced by MenABCWY as measured by hSBA performed with ACWY and 4 primary MenB test strains, 1 month after a booster vaccination in Groups 1 and 3.
- To describe the immune response induced by bivalent rLP2086, as measured by hSBA performed with 4 primary MenB test strains, 2 expressing an rLP2086 subfamily A protein and 2 expressing an rLP2086 subfamily B protein, measured 1 month after the booster vaccination in Groups 2 and 4.

#### 2.1.4. Secondary Safety Objectives

- To describe the safety profile of MenABCWY as measured by local reactions, systemic events, AEs, SAEs, NDCMCs, MAEs, and immediate AEs, after Vaccinations 1 and 2 in the ACWY-naïve and ACWY-experienced subjects separately.

#### 2.1.5. Exploratory Objectives

- To describe the immune response induced by MenACWY-CRM as measured by hSBA performed with ACWY test strains, 1 month after a booster vaccination in Groups 2 and 4.
- To describe the immune response induced by bivalent rLP2086 as measured by hSBA performed with 4 primary MenB test strains, 2 expressing an rLP2086 subfamily A protein and 2 expressing an rLP2086 subfamily B protein, measured 1 month after the first vaccination, in the bivalent rLP2086 arms (Group 2 and 4 subjects) combined.
- To further describe the immune response induced by MenABCWY compared to the immune response induced by MenACWY-CRM and bivalent rLP2086, as measured by hSBA performed with ACWY test strains and 4 primary MenB test strains, 2 expressing an LP2086 subfamily A protein and 2 expressing an LP2086 subfamily B protein, at blood sampling time points prior to the booster vaccination (Stage 2).
- To further describe the immune response induced by MenABCWY, as measured by hSBA performed with ACWY and 4 primary MenB test strains, 1 month after a booster vaccination in Groups 1 and 3.
- To further describe the immune response induced by bivalent rLP2086, as measured by hSBA performed with 4 primary MenB test strains, 2 expressing an LP2086 subfamily A protein and 2 expressing an LP2086 subfamily B protein, measured 1 month after the booster vaccination in Groups 2 and 4.

The endpoints (specified in [Section 3.3](#)) related to the exploratory objective to further describe the immune response induced by MenABCWY compared to the immune response induced by MenACWY-CRM and bivalent rLP2086, as measured by hSBA performed with ACWY test strains and 4 primary MenB test strains, 2 expressing an LP2086 subfamily A protein and 2 expressing an LP2086 subfamily B protein, at blood sampling time points prior to the booster vaccination (Stage 2) are not planned to be reported.

The endpoints (specified in [Section 3.3](#)) related to the exploratory objective to further describe the immune response induced by bivalent rLP2086 and MenABCWY for the proportions of subjects with hSBA titers  $\geq 1:4$ ,  $\geq 1:8$ ,  $\geq 1:16$ ,  $\geq 1:32$ ,  $\geq 1:64$ , and  $\geq 1:128$  for each of the 4 primary MenB and ACWY test strains and the endpoints of the proportion of subjects who achieve the 5 MenB endpoints 1 month after the booster vaccination are not planned to be reported.

## 2.2. Study Design

### 2.2.1. Description

This is a Phase 3, randomized, active-controlled, observer-blinded multicenter trial in which approximately 1590 subjects will be randomly assigned to receive either MenABCWY (Trumenba+meningococcal polysaccharide groups A, C, W-135, and Y tetanus toxoid conjugate vaccine [MenACWY-TT] reconstituted) and saline or bivalent rLP2086 and MenACWY-CRM. All subjects will be naïve to any meningococcal group B vaccine prior to enrollment.

Randomization will be stratified by prior vaccination history; approximately 795 ACWY-naïve subjects and 795 ACWY-experienced (having received 1 prior dose of vaccine containing 1 or more ACWY groups  $\geq 4$  years prior to the date of randomization) subjects will be enrolled.

Randomization will also be stratified by geographic region. Approximately 1320 subjects from United States (US) investigator sites and 270 subjects from ex-US countries will be randomized. Regional stratification will ensure sufficient population representation. The study is powered to meet the primary objective for immunogenicity based upon US subjects alone and additionally for the US and ex-US subjects.

The study will be conducted in 2 stages:

- Stage 1: comprises visits from study entry (Visit 1) through Visit 6. A pilot cohort consisting of 10 subjects 18 to <26 years of age will initially be enrolled and assigned to either Group 1 or 3, depending on prior vaccination history, and will receive MenABCWY at Vaccination 1. Seven days after the last pilot cohort subject has received MenABCWY, 7-day electronic diary (e-diary) and AE data will be summarized for review by the sponsor's independent review committee (IRC). No further enrollment will be permitted until review of these safety data is complete. If the IRC finds the safety data from the pilot cohort acceptable, enrollment will be opened to all ages and randomization groups, and the pilot cohort subjects will proceed in the study as planned. During Stage 1, the sponsor will be blinded to vaccine assignment beyond the completion of pilot cohort enrollment.

Subjects will receive 2 vaccinations, their first at the randomization visit (Visit 1) and a second vaccination at Month 6 (Visit 3). In support of assay development, a subset of approximately 600 subjects 18 to 25 years of age will have approximately 100 mL, rather than 20 mL, of blood drawn at Visits 1, 2, and 4; a subset of up to approximately 150 subjects 18 to 25 years of age will have up to 100 mL, rather than 20 mL, of blood drawn at Visit 11. Stage 1 will be observer-blinded. See [Table 2](#).

- Stage 2: from Months 18 to 60 (Visits 7 to 12). Subjects from both ACWY-naïve and ACWY-experienced strata will participate in Stage 2 (approximately 132 subjects from each of Groups 1 and 3 and approximately 65 subjects from each of Groups 2 and 4). Stage 2 will be open label. See [Table 3](#).

In Stage 2, the total number subjects for Groups 1 and 3 combined will be approximately 264 and the total number of subjects for Groups 2 and 4 combined will be approximately 130.

### 2.2.2. Number of Subjects

Approximately 1590 subjects (1320 from US sites and 270 from ex-US sites) will be randomized to participate in this study. A minimum total of 880 subjects will be enrolled from US sites to receive bivalent rLP2086+MenACWY-CRM to meet the postmarketing approval commitment (PAC) requirements.

Subjects will be stratified into 1 of 2 groups depending on their ACWY vaccination history: ACWY-naïve and ACWY-experienced. A total of 795 subjects will be enrolled into each stratum. All subjects in the study will be naïve to any meningococcal serogroup B vaccine at randomization.

Subjects will further be randomized into 2 vaccine groups within each stratum. Subjects randomized to Group 1 or 3 will be given MenABCWY and subjects randomized to Group 2 or 4 will be given bivalent rLP2086+MenACWY-CRM. A pilot cohort consisting of 10 subjects 18 to <26 years of age will first be enrolled into the study in Group 1 or 3 depending on ACWY history. These 10 subjects will be enrolled by US sites and vaccination will be open label.

Subjects from both ACWY-naïve and ACWY-experienced strata, approximately 132 from each of Groups 1 and 3 and approximately 65 from each of Groups 2 and 4, will participate in Stage 2.

A subset of 540 subjects will be randomly selected (composed of 450 subjects from US sites and 90 subjects from ex-US sites) from Groups 2 and 4 and will have secondary test strains assayed so that 125 evaluable subjects in US and 25 evaluable subjects from ex-US sites for each subset will be obtained. A total of 3 subsets will be included. Each subset will include 150 subjects from US sites and 30 subjects from ex-US sites to be assayed. In the first 2 subsets, subjects will each be assayed for 3 secondary test strains and the subjects in the last subset will be assayed for 4 secondary test strains. Therefore, not all subjects in the subsets will be tested for all 10 secondary strains. The subset for the secondary strain testing will be randomly selected to allow the 540 subjects from Groups 2 and 4 across the 3 subsets; the independent statistical center (ISC) will randomly allocate the 540 subjects from Groups 2 and 4 across the 3 subsets.

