7.2.2.1. MenB Serum Bactericidal Assays

For assessment of the immune response to bivalent rLP2086 and the B component of MenABCWY, 4 primary MnB test strains, PMB80 (A22), PMB2001 (A56), PMB2948 (B24), and PMB2707 (B44), will be used in the hSBAs for determination of the immunogenicity endpoints in this study.

Validated hSBA LODs and LLOQs for the 4 primary strains are shown below.

Table 4. Validated hSBA LODs and LLOQs for the 4 Primary MenB Strains

Strain Variant	LOD	LLOQ
A22	1:4	1:16
A56	1:4	1:8
B24	1:4	1:8
B44	1:4	1:8

Abbreviations: hSBA = serum bactericidal assay using human complement; LLOQ = lower limit of quantitation; LOD = limit of detection; MenB = *Neisseria meningitidis* group B.

Ten (10) secondary test strains will be used to perform hSBA testing so that at least 150 (125 from US investigative sites and 25 from other investigative sites) evaluable post-Vaccination 2 hSBA results are available for each secondary test strain. The hSBA assays for the 10 secondary test strains will be performed on up to 750 subjects (up to 600 subjects from US investigative sites and up to 150 subjects from other investigative sites, as described in Step 2 below) from Groups 2 and 4, combined.

Step 1: The 10 secondary test strains will be allocated across the 3 subsets. The first 2 subsets will each include 3 secondary test strains and the last subset will include 4 secondary test strains.

Step 2: Once all subjects have completed enrollment (Visit 1), the independent statistical center (ISC; a statistical team not involved in the conduct of the study) will randomly allocate up to 600 US subjects (up to 200 per subset) and up to 150 subjects (up to 50 per subset) from other investigative sites from Groups 2 and 4 across the 3 subsets.

Among the Group 2 and 4 subjects, a maximum of 8 test strains (up to 4 additional test strains and 4 primary test strains) may be tested.

Stage 1 sera obtained prior to the first vaccination with bivalent rLP2086 and 1 month after the second vaccination with bivalent rLP2086 (Visit 4) will be used for hSBA testing on the 10 secondary test strains.

hSBAs have been qualified for the 10 secondary test strains.

Qualified hSBA LODs and LLOQs for the 10 secondary strains are shown below.

Table 5. Qualified hSBA LODs and LLOQs for the 10 Secondary MenB Strains

Strain Variant	LOD	LLOQ
A29	1:4	1:8
A06	1:4	1:16
A12	1:4	1:16
A07	1:4	1:8
A15	1:4	1:8
A19	1:4	1:16
B16	1:4	1:8
B09	1:4	1:8
B03	1:4	1:8
B15	1:4	1:8

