The study sample size is mainly based on hypothesis-testing criteria to verify the clinical benefit of a 2-dose schedule for the use of bivalent rLP2086 administered at Months 0 and 6 in healthy subjects 10 years to <26 years of age in both Group 2 and Group 4. Given the observed response proportions from Study B1971012 for each endpoint, with 900 evaluable subjects, the primary objective based on all 5 primary endpoints will be met with a power of 95.2% (Table 12). Furthermore, with 748 evaluable subjects from US sites, the LCI criteria for the primary objective will also be met with a power of 89.9%. For the global study, assuming that ~85% of enrolled subjects qualify for the evaluable immunogenicity population, ~1060 subjects should be enrolled to receive bivalent rLP2086 and MenACWY-CRM. This assumes that every subject has sufficient sera for the 4 hSBAs.

Table 12. Overall Power to Meet the Primary Objectives

	Primary Endpoint Test Strain (Variant)	LCI Criteria	Study B1971012 0- and 6-Month Responses With 95% Confidence Interval (%) ^a	Number of Evaluable Subjects	Power
hSBA titer fold rise ≥4 from baseline	PMB80 (A22)	LL of 95% CI >75%	82.3 (76.3, 87.3)	900	99.97%
	PMB2001 (A56)	LL of 95% CI >85	90.1 (85.1, 93.8)	900	99.60%
	PMB2948 (B24)	LL of 95% CI >55	64.5 (57.4, 71.1)	900	99.99%
	PMB2707 (B44)	LL of 95% CI >60	66.0 (58.9, 72.6)	900	95.7%
Composite response (hSBA titer ≥ LLOQ for all 4 primary strains combined)		LL of 95% CI >65	72.9 (65.9, 79.1)	900	99.92%
Overall power					95.2%

Abbreviations: hSBA = serum bactericidal assay using human complement; LCI = lower limit of the confidence interval; LL = lower limit; LLOQ = lower limit of quantitation.

a. The power calculation was based on Study B1971012 with a vaccine schedule of 0 and 6 months.

An additional 530 subjects will be enrolled in the MenABCWY-MenABCWY regimen. Assuming 85% evaluable subjects, there will be 450 evaluable subjects in this regimen. These subjects will be further split between ACWY-naive and ACWY-experienced strata.

Given 530 subjects receiving at least 1 dose of MenABCWY, the probability of observing at least 1 AE will be 93.0% with a true incidence of 0.5% (see Table 13).

Table 13. Probabilities of Detecting AEs at Specified Incidences

Sample Size	True Incidence of AE	Probability of at Least 1 AE
530	0.01%	5.2%
530	0.10%	41.2%
530	0.25%	73.5%
530	0.50%	93.0%
530	1.00%	99.5%

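### SAP 2.2.2 fixes the secondary-strain draw at 150 US + 30 ex-US per subset, which leaves almost no margin for the protocol's requirement of at least 150 (125 + 25) evaluable results per strain

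*SAP*

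**What the plan says.** Protocol 7.2.2.1 sets the size of the secondary-strain testing in Groups 2 and 4 "so that at least 150 (125 from US investigative sites and 25 from other investigative sites) evaluable post-Vaccination 2 hSBA results are available" for each of the 10 strains. The strains are divided over three subsets of subjects (3, 3 and 4 strains). The independent statistical center "will randomly allocate up to 600 US subjects (up to 200 per subset) and up to 150 subjects (up to 50 per subset") from other sites, at most 750 in all. This takes place "Once all subjects have completed enrollment (Visit 1"), so before anyone's evaluability at Visit 4 is known.

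SAP 2.2.2 keeps the target, "so that 125 evaluable subjects in US and 25 evaluable subjects from ex-US sites for each subset will be obtained", but replaces the upper limits with fixed numbers: "A subset of 540 subjects will be randomly selected (composed of 450 subjects from US sites and 90 subjects from ex-US sites"), and "Each subset will include 150 subjects from US sites and 30 subjects from ex-US sites to be assayed". It gives no reason for the smaller number and no rule for a subset that falls short.

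The only planning rate in either document is in Protocol 9.1, "assuming that ~85% of enrolled subjects qualify for the evaluable immunogenicity population". That section adds: "This assumes that every subject has sufficient sera for the 4 hSBAs".

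**The concern.** The protocol states a minimum and provides headroom to reach it. The SAP keeps the same target figures but removes the headroom, so the draw is sized to its expected yield. When the expected count sits just above the target, chance alone will often leave the count short. The target also applies in two regions and three subsets, which makes six counts. At stake is whether the stated size of a secondary objective is delivered, and whether the two governing documents describe the same selection.

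**Working it through.** **Inputs**
- Targets: 125 US and 25 other per strain, 150 in total (Protocol 7.2.2.1; same split in SAP 2.2.2).
- SAP draw: 150 US + 30 ex-US per subset, three subsets (SAP 2.2.2).
- Protocol ceiling: 200 + 50 per subset (Protocol 7.2.2.1).
- Evaluable rate: about 85% (Protocol 9.1). Subjects are treated as independent, and 80% to 90% is shown as a range.

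**Step 1: reproduce the SAP's figures.** Divide each target by the evaluable rate and round up:
- 125 / 0.85 = 147.1, so 148 (SAP: 150).
- 25 / 0.85 = 29.4, so 30 (SAP: 30).
- The same rule gives 900 / 0.85 = 1059, the protocol's approximately 1060.

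The SAP's numbers are therefore consistent with ordinary inflation for expected yield. The expected yields are 150 × 0.85 = 127.5 and 30 × 0.85 = 25.5.

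**Step 2: chance of reaching the targets.** Let X be binomial(n, p). The chance per region is P(X ≥ target). Multiply the two regions for one subset, then cube for three subsets. At p = 0.85:
- US: P(X ≥ 125 of 150) = 0.758.
- Ex-US: P(X ≥ 25 of 30) = 0.711.
- Both in one subset: 0.758 × 0.711 = 0.539.
- Both in all three: 0.539³ = 0.156.
- Total only: P(X ≥ 150 of 180) = 0.771 in one subset; 0.771³ = 0.458 in all three.

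Sampling without replacement from 880 US subjects (748 evaluable) and 180 ex-US subjects (153 evaluable) gives 0.137 for all six targets, close to 0.156.

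**Step 3: dependence on the evaluable rate**

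| Evaluable rate | Both targets, one subset | Both targets, all three subsets |
|---|---|---|
| 80% | 0.077 | 0.0005 |
| 85% | 0.539 | 0.156 |
| 87% | 0.751 | 0.423 |
| 88% | 0.827 | 0.566 |
| 90% | 0.923 | 0.787 |

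**Step 4: loss of assay results.** The 85% rate assumes enough serum for the four primary assays, while these subjects need three or four more. The documents give no figure for that loss. If a further 1%, 2% or 5% of results per strain were lost (an assumption), the chance of meeting both targets for a given strain falls from 0.54 to 0.44, 0.34 or 0.12.

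**Step 5: how much margin is enough.** At 85%, 160 US + 36 ex-US per subset gives 0.992 and 0.995 per target, and (0.992 × 0.995)³ = 0.96 for all six. At the full ceiling of 200 + 50, the chance for all six exceeds 0.9999 at 80%, 85% and 90%.

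**Step 6: effect on the results.** At 85%, the 5th percentile of the evaluable count out of 180 is 145 and the 1st is 141. With an assumed response of 80%, the half-width of the Clopper-Pearson 95% interval is 6.7 points at n = 150, 6.8 at 145 and 6.9 at 140.

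**The case against.** Four points can fairly be made for the plan.

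- **No calculation or consistency error.** A reader might infer that 150 and 30 are miscalculated, or that the SAP contradicts the protocol. Neither is supported. The numbers follow from the documents' own inflation rule, and 200 + 50 is an upper limit that 150 + 30 respects. The SAP may also modify protocol plans (Protocol 9; SAP 2). This stands in full.
- **Only the protocol states a minimum.** Its wording attaches to the total of 150, with the regional split in parentheses; the SAP says only that the numbers will be obtained. This stands, and is why the figures for the total alone (0.77 and 0.46) are given beside the regional ones.
- **The targets are not simply likely to be missed.** Each regional target taken singly is more likely met than missed, as are both together in one subset. A probable miss holds only for all subsets jointly, and it reverses at about 88% evaluable. The 85% rate refers to membership of the evaluable immunogenicity population. Protocol 7.2.2.1 does not define an evaluable result that way, and SAP Table 18 also analyses these strains in the Stage 1 mITT population, so the relevant yield could be higher. This stands as uncertainty about the rate; Step 4 shows a loss in the other direction.
- **Little depends on it.** Protocol 9.2.2 makes these analyses descriptive, with no test or success criterion tied to 150. This stands and limits the severity.

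None of this supplies the missing margin. The SAP keeps the protocol's target figures while giving up the means of securing them.

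**Conclusion.** The point holds as a minor one. The SAP's fixed draw gives an expected yield just above the target and does not reliably deliver the protocol's minimum. At 85% evaluable, there is about an 84% chance (1 − 0.156) that at least one of the six regional targets is missed, and about a 54% chance (1 − 0.458) that at least one subset falls below 150 in total. These figures rest on independent subjects and on applying the 85% planning rate to secondary-strain results. A reader might infer that the secondary-strain conclusions are at risk. The documents do not support that: a likely shortfall is a few subjects per strain and widens a descriptive interval by 0.1 to 0.2 points on either side.

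**What to change.** Reconcile SAP 2.2.2 with Protocol 7.2.2.1 in one of two ways.

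1. **If selection is still open:** have the independent statistical center draw randomly ordered lists within the protocol's ceiling of 200 US + 50 other per subset. Test in list order until each strain has 125 + 25 evaluable Visit 4 results. If a fixed number is preferred, about 160 + 36 per subset would do at 85% evaluable.
2. **If 540 is kept or selection is already done:** restate 125 + 25 as an expected number and report the achieved count per strain and region. This may well be the case, since the current SAP version is dated February 2022 and SAP 3.5.2.2 refers to Stage 1 reporting in the past tense.

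The first option costs SAP wording and a modest number of extra assays on sera that the protocol already collects at Visits 1 and 4. The second costs wording only. Neither needs new subjects or visits.
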